8.3.2.2. Symptom Severity & Change

Patient Reported Outcomes Statistical Analyses: Symptom Severity & Change
Secondary Endpoint(s)

 Change from Baseline at Weeks 8, 12, 28, 52 by domain and single item on the CKD-AQ Change from Baseline at Weeks 8,12, 28, 52 in PGI-S
Exploratory Endpoint(s)

 Shift tables (Baseline to Weeks 8, 12, 28, and 52) in PGI-S N (%) of patients within each PGI-C symptom change level at Weeks 8, 12, 28, 52
Model Specification

 Scoring for the PGI-S, PGI-C, and CKD-AQ parameters is outlined in Section 10.6.5. The mean change from baseline in PGI-S, CKD-AQ domain and single item scores will be analyzed using an MMRM approach with an unstructured covariance matrix to compare the difference in means between arms. The models will be fitted to data collected after baseline up to Week 52. The model will include factors for treatment, time, prognostic randomization stratification factors, baseline PGI-S score value and the baseline PGI-S score by time and treatment by time interaction terms. Analyses will be done with the MIXED procedure in SAS, using the Kenward-Roger option to estimate denominator degrees of freedom and standard errors.
Model Results Presentation

 PGI-S, CKD-AQ domain and single item scores will be summarized using mean, standard deviation, minimum, P25, median, P75, and maximum by treatment group at all scheduled visits. Change from baseline in PGI-S, CKD-AQ domain and single item scores will be summarized using mean, standard deviation, minimum, P25, median, P75, and maximum by treatment group at all scheduled visits. Bar graphs displaying mean baseline and at visit values for the Week 8, 12, 28, and 52 visits for the CKD-AQ domain and single item scores will be provided by treatment group For the MMRM analyses of change from baseline in PGI-S, CKD-AQ domain and single item scores, an LSMEANS statement will provide adjusted treatment group means and standard errors and a point estimate and two-sided 95% confidence interval for the adjusted mean


Patient Reported Outcomes Statistical Analyses: Symptom Severity & Change
 
treatment difference (daprodustat – darbepoetin alfa) and a one-sided superiority p-value for this test at Weeks 8, 12, 28, and 52.
 
 • Additionally, shift tables by treatment group will be generated that display the number and percentage of subjects in each PGI-S category at baseline and the resulting PGI-S category at each scheduled visit. • Stacked bar charts will be produced by treatment group that display the percentage of subjects with each PGI-S response at baseline and Weeks 8, 12, 28 and 52. • The number and percentage of subjects in each PGI-C category at each scheduled visit will be summarized.

Model Results Interpretation
 
 • One-sided p-values will be compared to 0.025 to assess nominal significance. • Clinically meaningful effects for PRO assessments will be specified in a separate reimbursement RAP.

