
 To compare daprodustat to darbepoetin alfa on BP 	
 Change from baseline in SBP, DBP and MAP at Week 52 and at end of treatment Number of BP exacerbation events per 100 patient years N (%) with at least one BP exacerbation event during study

 To compare daprodustat to darbepoetin alfa on the time to rescue (defined as permanently stopping randomized treatment and due to meeting rescue criteria) 	
 Time to stopping randomized treatment due to meeting rescue criteria

 To compare daprodustat to darbepoetin alfa on HRQoL and Utility score 	
 Mean change in SF-36 HRQoL scores (Physical Component Score [PCS], Mental Component Score [MCS] and 8 health domains) between baseline and Weeks 8, 12, 28, 52, of particular interest are the changes from baseline in the vitality and physical functioning domains at Weeks 28 and 52 Change from baseline in Health Utility (EQ-5D-5L) score

Objectives	Endpoints
	at Week 52 
 • Change from baseline in EQ VAS at Week 52

 • To compare daprodustat to darbepoetin alfa on the symptom severity and change 	
 • Change from Baseline at Weeks 8, 12, 28, 52 by domain and overall symptom score on the CKD-AQ • Change from Baseline at Weeks 8, 12, 28, 52 in PGI-S

 • To compare daprodustat to darbepoetin alfa on renal function 	
 • eGFR change from baseline at Week 52
Exploratory Objectives	Exploratory Endpoints (statistical testing not planned)

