
 To further compare daprodustat to darbepoetin alfa on the symptom severity and change 	
 Shift tables (Baseline to Weeks 8, 12, 28, & 52) in PGI-S N(%) of patients within each PGI-C symptom change level at Weeks 8, 12, 28, 52. Change from baseline at Weeks 8, 12, 28, 52 by item on the CKD-AQ

 To further compare daprodustat to darbepoetin alfa on work productivity and regular daily activity impairment 	
 N (%) of patients currently employed at Baseline, Weeks 8, 12, 28, 52, yearly, EOS on the WPAI-ANS-CPV Percent work time missed at Baseline, Weeks 8,12, 28, 52, yearly, EOS on the WPAI-ANS-CPV

Objectives	Endpoints
	
 • Change from baseline in percent work time missed at Weeks 8, 12, 28, 52, yearly and EOS on the WPAI-ANS-CPV • Percent impaired (equivalent) at Baseline, Weeks 8,12, 28, 52, yearly, EOS on the WPAI-ANS-CPV • Change from baseline in percent impaired (equivalent) at Weeks 8, 12, 28, 52, yearly and EOS on the WPAI-ANS-CPV • Overall percent work impairment (equivalent) at baseline, Weeks 8,12, 28, 52, yearly, EOS on the WPAI-ANS-CPV • Change from baseline in overall percent work impairment (equivalent) at Weeks 8, 12, 28, 52, yearly, EOS on the WPAI-ANS-CPV • Percent activity impairment at Baseline, Weeks 8,12, 28, 52, yearly, EOS on the WPAI-ANS-CPV • Change from baseline in percent activity impairment at Weeks 8, 12, 28, 52, yearly, EOS on the WPAI-ANS-CPV
Safety Objective	Safety Endpoints

 • To compare the safety and tolerability of daprodustat to darbepoetin alfa 	
 • Incidence and severity of AEs and serious adverse events (SAEs) including AEs of special interest⁴ • Reasons for discontinuation of randomized treatment • Absolute values and changes from baseline in laboratory parameters, BP and heart rate

Conversion from g/dL to g/L is 1:10 and from g/dL to mmol/L is 0.6206. For example, Hgb of 10 to 11 g/dL is equivalent to 100-110g/L or 6.2 to 6.8 mmol/L.

1. Progression of CKD defined as: 40% decline in estimated glomerular filtration rate (eGFR) from baseline (confirmed 4-13 weeks later) OR end stage renal disease (ESRD) as defined by either
 - a) initiating chronic dialysis for ≥ 90 days or,
 - b) not initiating chronic dialysis when dialysis is indicated or,
 - c) kidney transplantation.

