
 • The difference in change from baseline in BP (SBP, DBP, and MAP) at Week 52 will be analyzed with a mixed model repeated measures (MMRM) approach with an unstructured covariance matrix to compare the difference in means between arms. The models will be fitted to scheduled BP data collected after baseline up to Week 52. Models will be run two times: 
 ○ On-treatment BP values only, excluding values collected during the stabilization period (Randomization date + 1 day to <Week 28). ○ On-treatment BP values only, including values collected during the stabilization period. 
The models will include factors for treatment, time, prognostic randomization stratification factors (see Section 10.10.2), baseline BP parameter and the baseline BP parameter by time and treatment by time interaction terms. Analyses will be done with the MIXED procedure in SAS, using the Kenward-Roger option to estimate denominator degrees of freedom and standard errors. For analyses using on- and off-treatment values, subjects who withdraw from the study before Week 52 are considered to be missing at random and in the analysis using

Secondary Safety Statistical Analyses: Blood Pressure

on-treatment values only, subjects who permanently discontinue randomized treatment before Week 52 are assumed to be missing at random.

- The difference in change from baseline in BP (SBP, DBP, and MAP) at the derived end of treatment (see Section 10.6.4) will be analyzed with an ANCOVA model including terms for treatment, prognostic randomization stratification factors (see Section 10.10.2) and the corresponding baseline BP parameter. This analysis will be performed using on-treatment BP values only.
- The number of on-treatment BP exacerbation events per 100 patient years will be calculated (see Section 10.6.4). Confidence intervals for the rate per 100 patient years will also be reported. For within group rates and the ratio of model estimated exacerbation rates, the point estimates, two-sided 95% confidence intervals, and one-sided p-value for the treatment group comparison will be obtained using a negative binomial model with treatment and the prognostic randomization strata as covariates and the logarithm of time on-treatment as an offset variable.

Model Results Presentation

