8.3.2. Planned Patient Reported Outcomes Statistical Analyses

8.3.2.1. HRQoL and Utility Score

Patient Reported Outcomes Statistical Analyses: HRQoL and Utility Score
Secondary Endpoints Endpoint(s)

 • Mean change in SF-36 HRQOL scores (PCS, MCS and 8 health domains) between baseline and Weeks 8, 12, 28, 52, of particular interest are the changes from baseline in the vitality and physical functioning domains at Weeks 28 and 52 • Change from baseline in Health Utility (EQ-5D-5L) score at Week 52 • Change from baseline in EQ VAS at Week 52
Exploratory Endpoint(s)

 • Change from baseline in Health Utility (EQ-5D-5L) score at Weeks 8, 12, 29, 52, yearly, EOS • Change from baseline in EQ VAS at Weeks 8, 12, 28, 52, yearly, EOS
Model Specification

 • Scoring for the SF-36 parameters and EQ-5D parameters is outlined in Section 10.6.5. • The mean change from baseline in SF-36 HRQoL scores (PCS, MCS, and 8 health domains), EQ-5D-5L score, and EQ VAS score will be analyzed using an MMRM approach with an unstructured covariance matrix to compare the difference in means between arms. The models will be fitted to QoL data collected after baseline up to Week 52. The model will include factors for treatment, time, prognostic randomization stratification factors, baseline QoL parameter value and the baseline QoL parameter by time and treatment by time interaction terms. Analyses will be done with the MIXED procedure in SAS, using the Kenward-Roger option to estimate denominator degrees of freedom and standard errors.
Model Results Presentation

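### The MMRM for CKD-AQ change scores adjusts for baseline PGI-S instead of the score's own baseline, which costs precision on nominally tested outcomes

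*SAP*

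**What the plan says.** Section 8.3.2.2 puts three kinds of outcome under one model: "The mean change from baseline in PGI-S, CKD-AQ domain and single item scores will be analyzed using an MMRM approach". The terms are then fixed as follows: "The model will include factors for treatment, time, prognostic randomization stratification factors, baseline PGI-S score value and the baseline PGI-S score by time"; treatment by time completes the list. Nothing elsewhere in the SAP adds baseline CKD-AQ to this model.

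The model beside it, for SF-36, EQ-5D-5L and EQ VAS (Section 8.3.2.1), uses "baseline QoL parameter value and the baseline QoL parameter by time and treatment by time interaction terms". The blood pressure model (Section 8.2.2.2) uses "baseline BP parameter and the baseline BP parameter by time and treatment by time interaction terms". The eGFR model in Section 8.2.2.2 and the Week 52 Hgb model in Section 8.1.1.2 follow the same pattern.

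On endpoint status, Section 8.3.2.2 lists as secondary "Change from Baseline at Weeks 8, 12, 28, 52 by domain and single item on the CKD-AQ". The table in Section 2.2 has as secondary the change "by domain and overall symptom score on the CKD-AQ", and places among the exploratory endpoints "Change from baseline at Weeks 8, 12, 28, 52 by item on the CKD-AQ". Results are judged one-sided at 0.025 for nominal significance, and Section 2.2 states that secondary endpoints carry no multiplicity adjustment.

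**The concern.** The response is a change score. Whenever follow-up regresses on baseline with a slope below one, change is negatively related to its own baseline, and adjusting for that baseline removes the related variance. Section 8.3.2.2 instead adjusts CKD-AQ change for PGI-S, a single item with five severity levels, although CKD-AQ is scored 0-100 and has its own Day 1 value. PGI-S can stand in for baseline CKD-AQ only as far as the two are correlated.

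At stake are wider confidence intervals than necessary for three domains and four single items at Weeks 8, 12, 28 and 52, which is 7 x 4 = 28 comparisons. Any subject with CKD-AQ data but no baseline PGI-S would also drop out of the CKD-AQ models.

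There is a practical problem as well. A programmer who follows the text fits the wrong covariate, and one who guesses the intent departs from the prespecified model.

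**Working it through.** The SAP gives no SD, correlation or power for CKD-AQ, so there is no stated figure to reproduce. The check has two parts.

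**1. Baseline terms side by side**

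| SAP section | Outcome | Baseline terms |
|---|---|---|
| 8.1.1.2 | Hgb at Week 52 | own baseline, own baseline x time |
| 8.2.2.2 | SBP, DBP, MAP | own baseline, own baseline x time |
| 8.2.2.2 | eGFR | own baseline, own baseline x time |
| 8.3.2.1 | SF-36, EQ-5D-5L, EQ VAS | own baseline, own baseline x time |
| 8.3.2.2 | PGI-S | own baseline, own baseline x time |
| 8.3.2.2 | CKD-AQ domains and items | PGI-S baseline, PGI-S baseline x time |

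Only the last row departs from the pattern. The missing covariate is available: Section 10.5.2.1 defines a Day 1 baseline for CKD-AQ, the schedule in Section 10.2.1.2 collects it, and the change score cannot be formed without it.

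**2. Precision at one visit**

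Assumptions, none of them from the SAP:
- Baseline score Y0 and follow-up score Y1 have unit variance and correlation rho.
- Baseline PGI-S has absolute correlation r with Y0.
- PGI-S relates to Y1 only through Y0.

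The response is D = Y1 - Y0.

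- Residual variance adjusting for PGI-S: 2(1 - rho) - r^2(1 - rho)^2
- Residual variance adjusting for own baseline: 1 - rho^2
- Ratio: [2 - r^2(1 - rho)] / (1 + rho)

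At rho = r = 0.5 the numerator is 2 - 0.25 x 0.5 = 1.875 and the ratio is 1.875 / 1.5 = 1.25. The SE ratio is the square root, 1.12. A simulation at these values also gave 1.25.

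| rho | r | Variance ratio | SE increase |
|---|---|---|---|
| 0.3 | 0 | 2 / 1.3 = 1.54 | 24% |
| 0.3 | 0.5 | 1.825 / 1.3 = 1.40 | 18% |
| 0.5 | 0.5 | 1.875 / 1.5 = 1.25 | 12% |
| 0.7 | 0.5 | 1.925 / 1.7 = 1.13 | 6% |
| 0.8 | 0.7 | 1.902 / 1.8 = 1.06 | 3% |
| 0.8 | 0.9 | 1.838 / 1.8 = 1.02 | 1% |

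The first and last rows are the extremes over rho 0.3-0.8 and r 0-0.9. Under this model the ratio exceeds 1 exactly when (1 - rho) > r^2(1 - rho), that is, for every rho < 1 and |r| < 1.

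As an illustration in power, take a comparison with 90% power under own-baseline adjustment at one-sided 0.025. At a ratio of 1.25 its power is Phi[(1.960 + 1.282)/sqrt(1.25) - 1.960] = 83%. At a ratio of 1.10 it is 87%.

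**The case against.** The strongest reply is that this is a slip of drafting: a PGI-S paragraph to which CKD-AQ was added. Every comparable MMRM uses the outcome's own baseline, and the generic subgroup model in Section 10.10.1 refers simply to the baseline value. That is probably right about the origin, but it does not correct the text. Section 10.10.1 governs subgroup analyses, and none is planned for CKD-AQ.

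Three stronger readings are tempting, and the document does not support them.

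- A reader might infer that the treatment effect is biased. With complete data, randomization keeps the comparison unbiased. Chance imbalance in baseline CKD-AQ is random error that the standard error already reflects.
- A reader might infer a loss equal to discarding 20-30% of subjects. That comes from the ratio 2/(1 + rho), which is 1.43, 1.33 and 1.25 at rho = 0.4, 0.5 and 0.6. It requires PGI-S to recover essentially nothing, for example by correlating equally with baseline and follow-up CKD-AQ. Both instruments are completed on Day 1, so PGI-S plausibly tracks baseline CKD-AQ more closely than later values and removes part of the variance.
- A reader might count seven secondary outcomes. Only the three domains are secondary in both Section 2.2 and Section 8.3.2.2. Single items are secondary in the latter, while Section 2.2 lists CKD-AQ by item as exploratory.

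It is also fair to say that nominal comparisons in a study planned for 4500 subjects are unlikely to turn on an SE difference of this order. That limits the importance of the point but gives no reason to keep the wrong covariate.

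**Conclusion.** As written, the specification names the wrong covariate for CKD-AQ. The cost is precision: a variance ratio of 1.25 (SE +12%) at rho = r = 0.5, and 1.02 to 1.54 (SE +1% to +24%) over rho 0.3-0.8 and r 0-0.9. These sizes assume equal variances at baseline and follow-up, a single visit, and no link between PGI-S and follow-up other than through baseline CKD-AQ. The SAP supplies neither correlation, so no single figure can be claimed.

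The outcomes affected are the three CKD-AQ domains and the four single items, all tested nominally. The co-primary endpoints and the Holm family of principal secondary endpoints are unaffected. The point is worth correcting because the error is clear on the text and the remedy costs nothing, even though no main conclusion depends on it.

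**What to change.** In the model specification of Section 8.3.2.2, replace the two PGI-S baseline terms with the baseline value of the score being analysed and its interaction with time. Leave treatment, time, stratification factors and treatment by time as they are. The PGI-S model does not change.

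The cost is one phrase, with no new data or visits. It should be made before unblinding so that it is not a post hoc change to a prespecified model. The same edit is a good occasion to reconcile the status of the CKD-AQ single items between Sections 2.2 and 8.3.2.2.

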8.3.2.3. Work Productivity and Regular Daily Activity Impairment

Patient Reported Outcomes Statistical Analyses: Work Productivity and Regular Daily Activity Impairment

Exploratory Endpoint(s)
 
 • N (%) of patients currently employed at Baseline, Weeks 8, 12, 28, 52, yearly, EOS on the WPAI-ANS-CPV • Percent work time missed at Baseline, Weeks 8,12, 28, 52, yearly, EOS on the WPAI-ANS-CPV • Change from baseline in percent work time missed at Weeks 8, 12, 28, 52, yearly and EOS on the WPAI-ANS-CPV • Percent impaired (equivalent) at Baseline, Weeks 8,12, 28, 52, yearly, EOS on the WPAI-ANS-CPV • Change from baseline in percent impaired (equivalent) at Weeks 8, 12, 28, 52, yearly and EOS on the WPAI-ANS-CPV • Overall percent work impairment (equivalent) at baseline, Weeks 8,12, 28, 52, yearly, EOS on the WPAI-ANS-CPV • Change from baseline in overall percent work impairment (equivalent) at Weeks 8, 12, 28, 52, yearly, EOS on the WPAI-ANS-CPV • Percent activity impairment at Baseline, Weeks 8,12, 28, 52, yearly, EOS on the WPAI-ANS-CPV • Change from baseline in percent activity impairment at Weeks 8, 12, 28, 52, yearly, EOS on the WPAI-ANS-CPV

Model Results Presentation
 
 • The number and percentage of subjects or summary statistics (mean, standard deviation, minimum, P25, median, P75, and maximum), as appropriate will be provided by treatment group for each of the responses to the WPAI-ANS-CPV at Baseline, Weeks 8, 12, 28, 52, yearly, and EOS. • For the continuous responses to the WPAI-ANS-CPV, the change from baseline will be summarized by treatment group using mean, standard deviation, minimum, P25, median, P75, and maximum at Weeks 8, 12, 28, 52, yearly and EOS.

8.4. Biomarker Analyses

Blood samples will be collected as outlined in the Time and Events Table in Section 10.2.1 for potential future analysis of CV risk, inflammation and iron metabolism. If biomarker analysis is pursued, details will be included in a separate RAP.

8.5. Pharmacogenetics Analyses

Blood samples will be collected as outlined in the Time and Events Table in Section 10.2.1 for potential future pharmacogenetics (PGx) analysis of the response to daprodustat (GSK1278863). If PGx analysis is pursued, details will be included in a separate RAP.

8.6. Analyses Excluding Sites with Suspected Fraud

During the conduct of the study, one site was closed due to GCP issues including suspected fraud at the site. This site ID ^{PPD} [REDACTED], only had one randomized subject in this study, and the data from this subject will be included in the study displays. Due to the small number of subjects at this site, no additional analyses will be performed excluding the subjects from this site.

10. APPENDICES

Section	Appendix
RAP Section 4 : Analysis Populations	
Section 10.1	Appendix 1 : Protocol Deviation Management and Definitions for Per-Protocol Population
RAP Section 5 : General Considerations for Data Analyses & Data Handling Conventions	
Section 10.2	Appendix 2 : Time and Events
Section 10.3	Appendix 3 : Assessment Windows
Section 10.4	Appendix 4 : Treatment States & Phases
Section 10.5	Appendix 5 : Data Display Standards & Handling Conventions 
 • Study Treatment & Sub-group Display Descriptors • Baseline Definitions & Derivations • Reporting Process & Standards
Section 10.6	Appendix 6 : Derived and Transformed Data 
 • General • Study Population • Efficacy • Safety • Patient Reported Outcomes
Section 10.7	Appendix 7 : Premature Withdrawals & Handling of Missing Data 
 • Premature Withdrawals • Handling of Missing Data
Section 10.8	Appendix 8 : Values of Potential Clinical Importance 
 • Laboratory Values • Vital Signs
Section 10.9	Appendix 9 : Multicentre Studies
Section 10.10	Appendix 10 : Examination of Covariates and Subgroups
Section 10.11	Appendix 11 : Multiple Comparisons and Multiplicity
Section 10.12	Appendix 12 : Model Checking and Diagnostics for Statistical Analyses
Section 10.13	Appendix 13 : Pharmacokinetic Sub-study Analysis Plan
Section 10.14	Appendix 14 : ABPM Sub-study Analysis Plan
Other RAP Appendices	
Section 10.15	Appendix 15 : Abbreviations & Trade Marks

10.1. Appendix 1: Protocol Deviation Management and Definitions for Per-Protocol Population

10.1.1. Exclusions from Per-Protocol Population

Exclusions from the PP population include events that, if they should occur, might:

- Directly impact the hemoglobin efficacy endpoint; or
- Lead to permanent discontinuation of study treatment or study withdrawal and hence indirectly impact the efficacy endpoint by causing data to be missing.

The following criteria define the events which, if they occur prior to the end of the EP, may lead to exclusion of a subject from the PP population. Exclusions from the PP Population will be subject to blinded review by the study team. The study team will also review the listing of unique concomitant medication terms to identify the prohibited medications. These reviews will occur before database has been unblinded for analysis.

A subject meeting any of the following criteria may be excluded from the Per-Protocol population:

Number	Exclusion Description
01	Baseline HemoCue Hgb value outside of Randomization (Day 1) Hgb entry criteria range
02	Less than 5 out of 7 scheduled evaluable ¹ Hgb values ² from the EP
03	Non-compliance with randomized treatment (compliance category of under compliant or over compliant) during the EP, based on eCRF randomized medication exposure and compliance forms
04	Inadequate iron status during EP, defined as ferritin \leq 100 ng/mL on two consecutive scheduled visits or TSAT \leq 20% on two consecutive scheduled visits
05	Subject received prohibited medication ³ for more than two weeks during EP

NOTES:

1. See Section 10.6.3.
2. Based on central laboratory Hgb values. If central laboratory Hgb value is missing, a non-missing HemoCue Hgb value will be used.
3. Prohibited medications include strong inhibitors of CYP2C8 (e.g., gemfibrozil) and strong inducers of CYP2C8 (e.g., rifampin/rifampicin).

